10.7. Appendix 7: Contraceptive Guidance and Collection of Pregnancy Information

Definitions:

Woman of Childbearing Potential (WOCBP)

A woman is considered fertile following menarche and until becoming postmenopausal unless permanently sterile (see below).

Women in the following categories are not considered WOCBP:

1. Premenarchal
2. Premenopausal female with 1 of the following:
 - Documented hysterectomy
 - Documented bilateral salpingectomy
 - Documented bilateral oophorectomy
3. Postmenopausal female
 - A postmenopausal state is defined as no menses for 12 months without an alternative medical cause. A high follicle-stimulating hormone (FSH) level in the postmenopausal range may be used to confirm a postmenopausal state in women not using hormonal contraception or hormonal replacement therapy (HRT). However, in the absence of 12 months of amenorrhea, a single FSH measurement is insufficient.

Contraception Guidance:

Female Participants

Female participants of childbearing potential are eligible to participate if they agree to use a highly effective method or acceptable method of contraception consistently and correctly as described in [Table 10-1](#).

Table 10-1 Highly Effective and Acceptable Contraceptive Methods

Highly Effective Contraceptive Methods That Are User Dependent^a Failure rate of < 1% per year when used consistently and correctly	
Combined (estrogen- and progestogen-containing) hormonal contraception associated with inhibition of ovulation ^b 
 • Oral • Intravaginal • Transdermal 	
Progestogen-only hormonal contraception associated with inhibition of ovulation 
 • Oral • Injectable 	
Highly Effective Methods That Are User Independent^a	
Implantable progestogen-only hormonal contraception associated with inhibition of ovulation 
 • Intrauterine device (IUD) • Intrauterine hormone-releasing system (IUS) • Etonogestrel implant (ie, Nexplanon®) 	
Bilateral tubal occlusion	
Intrauterine copper contraceptive (ie, ParaGard®)	
Vasectomized Partner	
A vasectomized partner is a highly effective contraception method provided that the partner is the sole male sexual partner of the WOCBP and the absence of sperm has been confirmed. If not, an additional highly effective method of contraception should be used.	
Sexual Abstinence	
Sexual abstinence is considered a highly effective method only if defined as refraining from heterosexual intercourse during the entire period of risk associated with the study intervention. The reliability of sexual abstinence needs to be evaluated in relation to the duration of the study and the preferred and usual lifestyle of the participant.	
Acceptable Methods	
Acceptable birth control methods that result in a failure of more than 1% per year include:	

 • Progestogen-only oral hormonal contraception, where inhibition of ovulation is not the primary mode of action • Male or female condom with or without spermicide • Cap, diaphragm, or sponge with spermicide • Nonhormonal intrauterine device 	
A combination of male condom with either cap, diaphragm, or sponge with spermicide (double-barrier methods) are also considered acceptable, but not highly effective, birth control methods.	

^a Typical use failure rates may differ from those when used consistently and correctly. Use should be consistent with local regulations regarding the use of contraceptive methods for participants participating in clinical studies.

Pregnancy Testing:

- WOCBP should only be included after a confirmed menstrual period and a negative highly sensitive pregnancy test at screening and also a negative test on Day 1.
- Additional pregnancy testing may also be performed at any other study visit at the investigator's discretion and at the study exit visit, and as required locally.
- Pregnancy testing will be performed whenever a menstrual cycle is missed or when pregnancy is otherwise suspected.

Collection of Pregnancy Information:**Female Participants Who Become Pregnant**

- The investigator will collect pregnancy information on any female participant who becomes pregnant while participating in this study. Information will be recorded on the appropriate form and submitted to the sponsor within 24 hours of learning of a participant's pregnancy. The participant will be followed to determine the outcome of the pregnancy. The investigator will collect follow-up information on the participant and the neonate, and the information will be forwarded to the sponsor. Generally, follow-up will not be required for longer than 6 to 8 weeks beyond the estimated delivery date. Any termination of pregnancy will be reported, regardless of fetal status (presence or absence of anomalies) or indication for the procedure.
- While pregnancy itself is not considered to be an AE or SAE, any pregnancy complication will be reported as an AE or SAE. A spontaneous or elective abortion is always considered to be an SAE and will be reported as such. Any poststudy pregnancy-related SAE considered reasonably related to the study intervention by the investigator will be reported to the sponsor as described in Section 8.3.4. While the investigator is not obligated to actively seek this information in former study participants, he or she may learn of an SAE through spontaneous reporting.
- If a pregnancy is confirmed after the participant has received study intervention, the participant may choose to exit the study after appropriate safety follow-up or to remain in the study for all safety and efficacy follow-up assessments through the end-of-study visit.

CONFIDENTIAL

Protocol 1936-201-008 Amd 1

BOTOX

10.8. Appendix 8: Clinician Allergan Platysma Prominence Scale

C-APPS grades and descriptions are shown in Section [8.1.1, Table 8-1](#).

[figure not shown]

CONFIDENTIAL

Protocol 1936-201-008 Amd 1

BOTOX

10.9.

[figure not shown]

CONFIDENTIAL

BOTOX

Protocol 1936-201-008 Amd 1

[figure not shown]
CONFIDENTIAL

Protocol 1936-201-008 Amd 1

BOTOX

10.10. Appendix 10: Example Patient-Reported Outcomes Questionnaires, Descriptions, and Instructions

This appendix provides complete samples of each questionnaire; however, participants will provide responses in electronic tablets (ie, eCOA) at the site.

[figure not shown]

CONFIDENTIAL

Protocol 1936-201-008 Amd 1

BOTOX

[figure not shown]

CONFIDENTIAL

Protocol 1936-201-008 Amd 1

BOTOX

[figure not shown]

CONFIDENTIAL

Protocol 1936-201-008 Amd 1

BOTOX

[figure not shown]

CONFIDENTIAL

Protocol 1936-201-008 Amd 1

BOTOX

[figure not shown]

CONFIDENTIAL

Protocol 1936-201-008 Amd 1

BOTOX

[figure not shown]

CONFIDENTIAL

Protocol 1936-201-008 Amd 1

BOTOX

[figure not shown]

CONFIDENTIAL

Protocol 1936-201-008 Amd 1

BOTOX

[figure not shown]

CONFIDENTIAL

Protocol 1936-201-008 Amd 1

BOTOX

[figure not shown]

CONFIDENTIAL

Protocol 1936-201-008 Amd 1

BOTOX

[figure not shown]

CONFIDENTIAL

BOTOX

Protocol 1936-201-008 Amd 1

[figure not shown]

CONFIDENTIAL

Protocol 1936-201-008 Amd 1

BOTOX

[figure not shown]

CONFIDENTIAL

Protocol 1936-201-008 Amd 1

BOTOX

[figure not shown]

CONFIDENTIAL

Protocol 1936-201-008 Amd 1

BOTOX

[figure not shown]

CONFIDENTIAL

Protocol 1936-201-008 Amd 1

BOTOX

[figure not shown]

CONFIDENTIAL

Protocol 1936-201-008 Amd 1

BOTOX

[figure not shown]

CONFIDENTIAL

Protocol 1936-201-008 Amd 1

BOTOX

[figure not shown]

CONFIDENTIAL

Protocol 1936-201-008 Amd 1

BOTOX

10.11. Fitzpatrick Skin Phototype

Type	Description
I	Always burns easily; never tans (sensitive)
II	Always burns easily; tans minimally (sensitive)
III	Burns moderately; tans gradually (light brown) (normal)
IV	Burns minimally; always tans well (moderate brown) (normal)
V	Rarely burns; tans profusely (dark brown) (insensitive)
VI	Never burns; deeply pigmented (insensitive)

Source: [Federal Register 1999](#)

[figure not shown]
[figure not shown]

CONFIDENTIAL

Protocol 1936-201-008 Amd 1

BOTOX

11. References

CONFIDENTIAL

Protocol 1936-201-008 Amd 1

BOTOX

### 3.0 LIST OF ABBREVIATIONS

AE adverse event

ANCOVA analysis of covariance

C-APPS Clinician Allergan Platysma Prominence Scale

CMH Cochran-Mantel-Haenszel

EDC electronic data capture

IDR Independent Drug Reconstitutor

MCP Multiple Comparisons Procedure

MedDRA Medical Dictionary for Regulatory Activities

mITT Modified Intent-to-Treat

P-APPS Participant Allergan Platysma Prominence Scale

PDSOT possible distant spread of toxin

PRO patient-reported outcome

PT preferred term

SAE serious adverse event

SAP statistical analysis plan

SOC system organ class

TEAE treatment-emergent adverse event

WOCBP woman of childbearing potential

## 4.0 INTRODUCTION

This statistical analysis plan (SAP) provides a more technical and detailed elaboration of the statistical analyses of the efficacy and safety data as outlined and/or specified in the protocol of Study 1936-201-008 (Amendment 1 dated 12 August 2019). Specifications of tables, figures, and data listings will be provided in a separate document.

Analyses for patient-reported outcomes (PROs) will be specified in a separate document, and the results will be summarized in a separate report. However, analyses for the Participant Allergan Platysma Prominence Scale (P-APPS) will be described in this document.

Study 1936-201-008 is a Phase 2, multicenter, randomized, double-blind, placebo-controlled, parallel-group, dose-ranging study.
Platysma prominence will be assessed at maximum contraction by the investigator using the C-APPS and by the participant using the P-APPS.
The length of this study will be approximately 4 months for each participant. Signed informed consent from the participant will be obtained at Screening (Day -14 to Day -7) before any study-related procedures. After verification that the participant meets all inclusion and exclusion criteria, and completion of all baseline study procedures, the participant will be randomized in a 1:1:1 ratio to receive BOTOX® high dose, BOTOX low dose or placebo at Visit 2/Day 1.
After
randomization on Day 1, participants will return to the research facility at Days 7, 14, 30, 60, and 90 (Visits 3 to 7, respectively) for protocol-defined efficacy and safety assessments. Study exit protocol-defined assessments will occur at Day 120 (Visit 8) or at early termination.

The schedule of activities is presented in Table 4-1 (footnotes refer to sections within the protocol).

Table 4-1 **Schedule of Activities** 

	Visit 1	Visit 2	Visit 3	Visit 4	Visit 5	Visit 6	Visits 7	Visit 8
Study Procedures	Screening Day -14 to Day -7	Baseline/ Randomization/ Treatment Day 1 a	Day 7	Day 14	Day 30	Day 60	Day 90	Study Exit b Day 120
Visit Windows	-	-	± 3 Days	± 3 Days	± 3 Days	± 7 Days	± 7 Days	± 7 Days
Informed Consent, Privacy Authorization	X							
Inclusion/Exclusion Criteria	X	X						
Demographics	X							
Medical/Surgical History	X							
Weight	X	X	X	X	X	X	X	X
Fitzpatrick Skin Phototype d	X							
Abbreviated Physical Examination e	X							
Vital Signs f	X	X	X	X	X	X	X	X
Urine Pregnancy Test (WOCBP only)g	X	X						X
Standardized Photography	X	X	X	X	X	X	X	X
Self Assessment by Participants:								
Participant Allergan Platysma Prominence Scale (P-APPS)i		X	X	X	X	X	X	X

d

	Visit 1	Visit 2	Visit 3	Visit 4	Visit 5	Visit 6	Visits 7	Visit 8
Study Procedures	Screening Day -14 to Day -7	Baseline/ Randomization/ Treatment Day 1 a	Day 7	Day 14	Day 30	Day 60	Day 90	Study Exit b Day 120
Visit Windows	-	-	± 3 Days	± 3 Days	± 3 Days	± 7 Days	± 7 Days	±7 Days
Clinician Assessment:								
Clinician Allergan Platysma Prominence Scale (C-APPS)	X	X	X	X	X	X	X	X
Randomization		X						
Study Intervention Administration j		X						
Concomitant Medications/Procedures	X	X	X	X	X	X	X	X
Adverse Events k	X	X	X	X	X	X	X	X

a All baseline (Day 1) study procedures, including patient-reported outcome questionnaires, must be completed before randomization and study intervention.

Prepared by an Independent Drug Reconstitutor (IDR) and injected by the investigator. NOTE: The IDR must not perform any other study-related procedures.

Or early discontinuation from the study. All exit assessments should be completed as soon as possible after a decision to discontinue a participant from the study.

Fitzpatrick Skin Phototype is provided in Section 10.11 of the study protocol.

e An abbreviated physical examination will be completed at the screening visit and will include the investigator assessment of general appearance, head, ears, eyes, nose, throat, and neck.

Vital Signs (blood pressure, respiratory rate, pulse rate) will be taken while the participant is sitting for at least 5 minutes.

Woman of childbearing potential (WOCBP) must have a negative urine test result before receiving study intervention. A urine pregnancy test may also be performed at any other visit, at the investigator's discretion.

On Day 1, AEs will be collected prior to and after treatment. Participants will be observed at least 30 minutes after study intervention administration for AEs. In the case of an AESI, see Section 8.3.6 of the study protocol.

### 5.0 OBJECTIVE

The objective of this study is to evaluate the safety and efficacy of a high and low dose of BOTOX versus placebo in the treatment of participants with moderate to severe platysma prominence. See Section 3 of the protocol for additional details.

### 6.0 PARTICIPANT POPULATIONS

## 6.1 MODIFIED INTENT-TO-TREAT POPULATION

The modified intent-to-treat (mITT) population will consist of all randomized participants who had at least 1 post-baseline assessment of the primary efficacy parameter, the C-APPS, as described in the protocol.

### 6.2 SAFETY POPULATION

The safety population will consist of all participants who were administered study intervention.

## 7.0 PARTICIPANT DISPOSITION

The number of participants in the 2 study populations (safety and mITT) will be summarized by study intervention and overall.

The number of participants screened will be summarized overall. The number and percentage of participants who were randomized, who were treated, who completed the study or who prematurely discontinued will be presented for each study intervention group and pooled across study intervention groups for all screened participants. The reasons for discontinuation will also be summarized (number and percentage).

### 8.0 DEMOGRAPHICS AND OTHER BASELINE CHARACTERISTICS

Demographic parameters (age;	race;
ethnicity; sex), and baseline characteristics (weight; height;	
C-APPS grade; P-APPS grade; Fitzpatrick Sl	kin Phototype)
will be summarized descriptively by study intervention group for the mIT	Γ population.
Continuous variables will be summarized by number of participants, mean	ı, standard
deviation (SD), median, minimum, and maximum values. Categorical vari	ables will be
summarized by number and percentage of participants.	

Participants' medical and surgical histories will be coded using the Medical Dictionary for Regulatory Activities (MedDRA), version 23.0 or newer. The number and percentage of participants with medical and surgical histories ongoing at screening will be

summarized by system organ class (SOC) and preferred term (PT) in each study intervention group and overall for the mITT population. In addition, any concomitant procedures, defined as any procedure performed on or after the date of the first dose of study intervention, will be summarized by SOC and PT in each study intervention group for the mITT population.

Prior medication is defined as any medication taken before the date of the first dose of study intervention. Concomitant medication is defined as any medication taken on or after the date of the first dose of study intervention. The use of prior and concomitant medications will be summarized by drug class and drug name in each study intervention group for the mITT population.

### 9.0 EXTENT OF EXPOSURE AND TREATMENT COMPLIANCE

Participants will receive study intervention only on Day 1. The number of participants treated will be presented by the study intervention group:

- BOTOX high dose
- BOTOX low dose
- Placebo

If a subject does not receive the full dose, this will be indicated; significant deviations to dosing will be reported.

### 10.0 PROTOCOL DEVIATIONS

The number and type of significant protocol deviations will be summarized in total and by study intervention group for all randomized participants.

A listing of significant protocol deviations will be provided.

#### 11.0 EFFICACY ANALYSES

The efficacy analyses will be based on the mITT population. Observed data will be used for all analyses. Baseline for efficacy is defined as the last non-missing efficacy assessment before study intervention.

The following set of hypotheses will be used to compare the BOTOX groups with placebo for the primary endpoint analysis:

 Null hypothesis: BOTOX and placebo are equally effective in the probability of achieving ≥ 1-grade improvement in the C-APPS score from baseline at Day 14.

 Alternative hypothesis: BOTOX and placebo are not equally effective in the probability of achieving ≥ 1-grade improvement in the C-APPS score
 from baseline at Day 14.

The following set of hypotheses will be used to compare the BOTOX groups with placebo for the secondary endpoint analysis:

- Null hypothesis: BOTOX and placebo are equally effective in the probability of achieving ≥ 1-grade improvement in the P-APPS score from baseline at Day 14.
- Alternative hypothesis: BOTOX and placebo are not equally effective in the probability of achieving ≥ 1-grade improvement in the P-APPS score
   from baseline at Day 14.

For the primary endpoint analysis, the Cochran-Mantel Haenszel (CMH) test will be used to evaluate the equality of responder proportions of C-APPS between study intervention groups.

The BOTOX high dose group will be compared to the placebo group, and the BOTOX low dose group will be compared to the placebo group using a gate-keeping strategy (Dmitrienko 2005). If the comparison of the BOTOX high dose group versus the placebo group yields a p-value at the 0.05 significance level, the BOTOX low dose group will then be compared with the placebo group at the same 0.05 significance level. Otherwise, the BOTOX low dose group will not be considered statistically significantly superior to the placebo group, regardless of its p-value. (see Section 11.3.)

Similarly, for the secondary endpoint analysis, the statistical comparisons will be conducted for the P-APPS.

All statistical tests will be 2-sided hypothesis tests performed at the 0.05 level of significance for main effects. Wald confidence intervals for proportions of responders and difference in the proportion of responders will also be presented. All confidence intervals will be 2-sided 95% confidence intervals.

Continuous descriptive statistics include the following: the numbers of participants with non-missing values at both baseline and the specified post-baseline analysis visit, mean, SD, median, minimum, and maximum.

Categorical variables will be summarized by number and percentage of participants.

Efficacy analyses will be performed for all visits. The primary analysis timepoint is Day 14.

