### 11.2 SECONDARY EFFICACY ENDPOINTS

The secondary efficacy endpoint will be achievement of  $\geq$  1-grade P-APPS improvement from baseline on Day 14, as rated at maximum contraction by the participant using the P-APPS.

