# 11.3 MULTIPLE COMPARISONS PROCEDURE FOR PRIMARY AND SECONDARY ENDPOINTS

The overall familywise error rate (FWER) will be controlled at  $\alpha = 0.05$  for the set of primary and secondary endpoint comparisons between each of the BOTOX groups versus placebo. The overall serial gatekeeping multiple comparisons procedure (MCP) is defined as follows:

Table 11-1 Multiple Comparisons Procedure

MCP Step a	Endpoint	MCP Criteria
1	C-APPS responder (BOTOX high dose vs placebo)	Nominal p-value $\leq \alpha$
2	P-APPS responder (BOTOX high dose vs placebo)	Nominal p-value $\leq \alpha$
3	C-APPS responder (BOTOX low dose vs placebo)	Nominal p-value $\leq \alpha$
4	P-APPS responder (BOTOX low dose vs placebo)	Nominal p-value $\leq \alpha$

<sup>a Serial gatekeeping MCP only proceeds to next step if all endpoints are statistically significant after application of MCP criteria in previous and current MCP steps for a BOTOX group.

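### SAP 11.0 opens the low-dose C-APPS test after high-dose C-APPS alone, but SAP Table 11-1 and protocol Table 9-3 also require high-dose P-APPS

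*SAP*

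**What the plan says.** SAP 11.0 first deals with the primary endpoint, where the CMH "test will be used to evaluate the equality of responder proportions of C-APPS between study intervention groups". The next paragraph gives the gate: if high dose versus placebo reaches the 0.05 level, "the BOTOX low dose group will then be compared with the placebo group at the same 0.05 significance level"; if not, the low dose cannot be called superior, "regardless of its p-value. (see Section 11.3". P-APPS is not a condition anywhere in this rule. The secondary endpoint then gets one sentence: "Similarly, for the secondary endpoint analysis, the statistical comparisons will be conducted for the P-APPS".

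SAP 11.3 says "The overall serial gatekeeping multiple comparisons procedure (MCP) is defined as follows" and gives Table 11-1 with four steps, each at nominal p ≤ α:

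1. High-dose C-APPS
2. High-dose P-APPS, listed as "P-APPS responder (BOTOX high dose vs placebo"
3. Low-dose C-APPS
4. Low-dose P-APPS

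The table footnote lets testing proceed only on significance "after application of MCP criteria in previous and current MCP steps for a BOTOX group". Protocol 9.4.1.2, Table 9-3, has the same order and footnote, and counts all four comparisons in one family controlled at 0.05. The visible text of SAP 17.0 lists no change to the multiplicity procedure.

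**The concern.** The SAP contains two rules for the low-dose test on the primary endpoint. Under 11.0, low-dose C-APPS opens as soon as high-dose C-APPS succeeds. Under Table 11-1, high-dose P-APPS must succeed as well. The rules can part only when the high dose works on the investigator's scale but not on the participant's, and in that case the low-dose claim turns on which paragraph is followed. In a dose-ranging study that is a main comparison. If the text stays as it is, the sponsor could appear to have chosen between two pre-specified rules after seeing the results.

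The P-APPS sentence adds a second gap. It does not say whether P-APPS waits for C-APPS, so the familywise error rate under 11.0 depends on how the reader fills that in.

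**Working it through.** **Does the conclusion change?** Take illustrative p-values of 0.01 for high-dose C-APPS, 0.20 for high-dose P-APPS and 0.03 for low-dose C-APPS.

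- SAP 11.0: 0.01 ≤ 0.05, so low-dose C-APPS is tested; 0.03 ≤ 0.05, so it is significant.
- Table 11-1: step 1 passes, step 2 fails (0.20 > 0.05), testing stops, and low-dose C-APPS is not significant.

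**Inputs for the error rates**

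- Two-sided 0.05 per test, critical value 1.96 (SAP 11.0).
- Family of four comparisons, familywise error rate 0.05 (protocol 9.4.1.2; SAP 11.3).
- Allocation 1:1:1, about 55 per arm (protocol 9.2). With a shared placebo arm and equal group sizes, the two dose comparisons on one scale have correlation (1/n)/(1/n + 1/n) = 0.5.
- Correlation r between the C-APPS and P-APPS tests: not given in the documents, so assumed, over 0 to 0.9. Tests differing in both dose and scale then have correlation 0.5r.

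Write HC, HP, LC and LP for the high- and low-dose tests on C-APPS and P-APPS.

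**The plan's own figure.** In a fixed sequence, no false rejection can occur unless the first true null in the order is rejected, which has probability 0.05. Table 11-1 therefore holds 0.05, as the plan states.

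**Readings of 11.0**

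- *Unlinked:* HC then LC, and separately HP then LP. Under the global null the error is P(|HC| > 1.96 or |HP| > 1.96) with correlation r. At r = 0 this is 1 − 0.95² = 0.0975.
- *Hybrid:* HP is gated on HC, but LC still needs only HC. Under the global null every path starts at HC, so the rate is 0.050. If only HC has a true effect, its gate is open and the error is P(|LC| > 1.96 or |HP| > 1.96) with correlation 0.5r. The unlinked reading gives the same value in this case.
- *P-APPS last:* P-APPS is tested only after both C-APPS tests. This is again a single sequence, so 0.050.

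Exact values by bivariate normal integration:

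| r | Unlinked, global null | Unlinked or hybrid, only HC effective |
|---|---|---|
| 0 | 0.0975 | 0.0975 |
| 0.3 | 0.0951 | 0.0969 |
| 0.5 | 0.0907 | 0.0959 |
| 0.7 | 0.0835 | 0.0943 |
| 0.9 | 0.0704 | 0.0921 |

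If the high dose works on both scales and the low dose on neither, the hybrid reading gives 0.0975 falling to 0.0704 when LP is gated on HP alone, and 0.050 when LP is also gated on LC.

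**Footnote.** If its closing words are read as gating only within each dose, the chains are HC then HP, and LC then LP. Under the global null the error is P(|HC| > 1.96 or |LC| > 1.96) with correlation 0.5, which is 0.0907.

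**Simulation check.** There were 4,000,000 draws of the four z-statistics per value of r, with effective comparisons shifted by 8 SD, in seven configurations: global null; HC only; high dose on both scales; C-APPS at both doses; all but LP; HP only; P-APPS at both doses. The table order and the P-APPS-last order gave 0.0499 to 0.0502 throughout. The unlinked and hybrid values agreed with the exact ones to within 0.0003.

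**The case against.** The strongest reply is that the documents already show which text governs. Section 11.0 points to 11.3, 11.3 presents itself as the definition, the protocol has the same table, and both documents require 0.05 across the whole set. On that view 11.0 is an incomplete summary, and the inflated rates belong to readings the rest of the plan excludes. This stands as evidence of intent and keeps the point at the level of a wording correction. It does not remove the conflict: 11.0 states a complete if/then/otherwise rule, the section it cites states a different one, and nothing says which prevails.

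Several narrower objections also carry some weight:

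- The P-APPS-last reading of 11.0 does hold 0.05. It still contradicts Table 11-1.
- The figures above 0.05 rest on an assumed correlation. The wording conflict does not.
- A sentence in SAP 17.0 breaks off and the protocol's hypotheses section is not visible, so one can say only that no multiplicity change is visible.
- The within-dose reading of the footnote sits badly with a numbered serial procedure, and protocol Table 9-3 carries the same words. Tidying the footnote is secondary.
- Protocol 9.4.1.3 already applies CMH to both endpoints, so naming it for P-APPS in the SAP is a clarification.
- Only significance labels on later comparisons could change. No estimate or p-value does.

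**Conclusion.** The concern holds. SAP 11.0 is wrong as written: it omits the high-dose P-APPS condition that SAP Table 11-1 and protocol Table 9-3 both place before low-dose C-APPS. The table order gives the stated 0.05. Under the unlinked and hybrid readings of 11.0 the rate is 0.0921 to 0.0975 when only high-dose C-APPS has a true effect. The unlinked reading also gives 0.0704 to 0.0975 under the global null. These ranges assume a dose correlation of 0.5 and a between-scale test correlation of 0 to 0.9.

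Step 1, high-dose C-APPS, is unaffected under every reading. How likely the two rules are to disagree in this trial cannot be stated, because the design response rates are not visible. This should be fixed, but it does not threaten the main high-dose result.

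**What to change.** Before unblinding, replace the gatekeeping paragraph and the P-APPS sentence after it in SAP 11.0, keeping the literature citation, with:

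> P-APPS responders will be analysed with the same CMH method as C-APPS. The four comparisons are tested in the order of Table 11-1, each at two-sided 0.05; testing stops at the first p > 0.05 and later comparisons are descriptive.

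The first sentence is there because the visible SAP names CMH for C-APPS only. SAP 11.2 defines the secondary endpoint "as rated at maximum contraction by the participant using the P-APPS" and names no test. The sentence agrees with protocol 9.4.1.3.

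Delete the last four words of the Table 11-1 footnote, so that it cannot be read as gating within one dose. Add a line to SAP 17.0 recording the clarification and stating that the order and meaning of protocol Table 9-3 are unchanged; this also covers the small wording difference from the protocol's footnote.

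Cost: two sentences in 11.0, four words in one footnote and one line in 17.0. No protocol amendment, participants or new data are needed.
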